**Multicenter: University of Michigan ([name])**

**INSTRUCTIONS**

This template is intended to help investigators prepare a protocol that includes all of the necessary information needed by the IRB to determine whether a study meets approval criteria. **Read the following instructions before proceeding:**

1. Use this protocol template for a PI initiated study that includes direct interactions with research subjects. Additional templates for other types of research protocols are available in the system Library.
2. If a section or question does not apply to your research study, type “Not Applicable” underneath.
3. Once completed, upload your protocol in the “Basic Information” screen in IRES IRB system.

**SECTION I: RESEARCH PLAN****Section 1. Statement of Purpose:** State the scientific aim(s) of the study, or the hypotheses to be tested.

The coronavirus disease-19 (COVID-19) pandemic has caused significant distress, and grief around the world. Given the rising numbers of infected individuals in the United States (US) and need for hospitalization in at least 14% of infected patients (1), there is substantial strain on the health care system. Identifying ways to ameliorate the progression and severity of this infection and preventing hospitalization is critical in preventing break in capacity and overwhelming the healthcare system.

Currently, it is believed that COVID-19 infected patients undergo two phases of illness; viral replication and the more fatal phase of inflammation. Preventing the inflammatory phase has the potential to decrease hospitalization, use of ventilation and mortality. Accordingly, we are proposing to identify the role of resistant potato starch (a natural dietary supplement) in preventing the progression to the inflammatory phase through its immunomodulatory effects on the gut microbiome.

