**Primary Outcome Measure:**

Hospitalization for a COVID-19 related admission during the first month of follow up.

A COVID-19 related admission is defined as the following:

- Presenting symptoms of fever or shortness of breath or myalgia or cough or hypoxia.
- Admission diagnosis of hypoxic respiratory failure, pneumonia, viral pneumonia.
- Death prior to hospitalization thought to be secondary to COVID-19 will also be defined as an event.

All hospital admissions will be reviewed and adjudicated by site PI to ensure that the hospitalization is a COVID-19 related admission.

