### **Duration of Follow-Up**

Subjects will be followed for 4 months from positive COVID-19 test or until death, whichever occurs first. Subjects will be followed for adverse events for at least 30 days after the last dose of study drug. Subjects removed from treatment for persistent adverse events thought to be due to interventional treatment will be followed until resolution or stabilization of the adverse event

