### **Procedures during treatment and follow up procedures**

*Assessment for primary objective of hospitalization at one month via phone and EHR:*

Every 2 days phone questionnaires (**see attached questionnaire**) and EHR review for the first 14 days followed by once weekly phone call and EHR review to complete a month follow up from last dose of treatment.

*Assessment for secondary objectives of TTCA and symptom severity score via phone and EHR:*

Every 2 day phone questionnaires (**see attached questionnaire**) and EHR review for the first 14 days followed by once weekly phone call and EHR review to complete a month follow up from last dose of treatment.

*Assessment of exploratory objectives*

EHR review to complete 4 months follow up from COVID positive test

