Adverse event (AE) monitoring and reporting is a routine part of every clinical trial and is done to ensure the safety of subjects enrolled in the studies as well as those who will enroll in future studies using similar agents. Data on adverse events will be collected from the time of the initial study treatment through 30 days after the last dose. Any serious adverse event that occurs more than 30 days after the last study treatment and is considered related to the study treatment must also be reported. Serious Adverse Events (SAEs) will continue to be followed until:

- Resolution or the symptoms or signs that constitute the serious adverse event return to baseline;
- There is satisfactory explanation other than the study [treatment or intervention] for the changes observed; or
- Death.

The investigator is responsible for the detection, documentation, grading and assignment of attribution of events meeting the criteria and definition of an AE or SAE. The **definitions** of AEs and SAEs are given below. It is the responsibility of the principal investigator to ensure that all staff involved in the trial is familiar with the content of this section.

Any medical condition or laboratory abnormality with an onset date before initial study treatment is considered to be pre-existing in nature. Any known pre-existing conditions that are ongoing at time of study entry should be considered medical history.

All events meeting the criteria and definition of an AE or SAE, as defined below, occurring from the initial study treatment through 30 days following the last dose of study treatment must be recorded as an adverse event in the subject's source documents and on the CRF regardless of frequency, severity (grade) or assessed relationship to the study treatment.

In addition to new events, any increase in the frequency or severity (i.e., toxicity grade) of a pre-existing condition that occurs after the subject begins study treatment is also considered an adverse event.

Review of AE and SAE data will be performed on a routine basis by the Data and Safety Monitoring Board (DSMB).

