We will analyze the efficacy of RPS in relation to the primary outcome of hospitalization. If there is a significant difference between the two arm with p-value of <0.01, we will not continue the study. For data quality and integrity, we will also analyze the efficacy of RPS in relation to the secondary outcomes of TTCA and symptom severity score to assess efficacy and ensure no increase in harm in the intervention arm.

**Section 14. Statistical Considerations:** Describe the statistical analyses that support the study design.

**Study design/Study outcomes measures:** We will conduct a double-blinded, randomized clinical trial comparing RPS (~20g twice daily for 14 days) with placebo (non-resistant starch) in 1500 adults (age  $\geq 18$  years old) with COVID-19 diagnosis (defined by a positive swab) who are being managed in the outpatient setting. The primary outcome is hospital admission due to COVID-19 related complications. The secondary outcomes are TTCA and symptom severity score. We also will investigate some exploratory outcomes such as ER visits without admission, and among those hospitalized, we will explore differences in oxygen requirement, need for mechanical ventilation, duration of ventilation, length of hospital stay, levels of inflammatory markers routinely ordered as part of clinical care (CRP, LDH, D-dimer, Ferritin, IL-6), and rates of discharge between the RPS and placebo arms.

**Sample size and accrual:** Assuming a 14% admission rate in the placebo group, we calculated that a sample size of 1362 (we will enroll 1500 to account for 10% loss to follow up) will be required to provide 80% power (with a two-sided alpha level of 0.04 to detect an absolute reduction in hospital admission rates of 5% or more in the RPS group. **The primary analysis will be based on the intention-to-treat principle, with all patients included in their assigned group.**

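### No by-arm mortality comparison is specified despite follow-up to death or 4 months, and length of stay and ventilation time have no rule for death

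*Combined protocol and SAP*

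**What the plan says.** **Rationale.** Section 1 states: "Preventing the inflammatory phase has the potential to decrease hospitalization, use of ventilation and mortality".

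**Follow-up.** Under Duration of Follow-Up, "Subjects will be followed for 4 months from positive COVID-19 test or until death, whichever occurs first". The assessment listed for the exploratory objectives is "EHR review to complete 4 months follow up from COVID positive test", and Table 4 schedules EHR review at days 60, 90 and 120.

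**Primary outcome.** It is "Hospitalization for a COVID-19 related admission during the first month of follow up". On death, the definition adds only: "Death prior to hospitalization thought to be secondary to COVID-19 will also be defined as an event".

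**Exploratory outcomes.** Among those hospitalized, Section 14 and Exploratory Objectives list "need for mechanical ventilation, duration of ventilation, length of hospital stay, levels of inflammatory markers routinely ordered as part of clinical care", and the Section 14 sentence ends "and rates of discharge between the RPS and placebo arms". No handling of death is given for any of them.

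**Safety.** Section 11 collects adverse events from first treatment to 30 days after the last dose, whatever the assessed relationship. An SAE that "occurs more than 30 days after the last study treatment and is considered related to the study treatment must also be reported". Fatal disease progression is an SAE, and so is an inpatient admission of at least 24 hours. SAEs are followed to resolution, a satisfactory explanation other than the study treatment, or death. The DSMC report contains aggregate tables and listings of SAEs, with no split by arm stated. Safety analyses cover participants who received at least one dose.

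**Status of late follow-up.** Protocol Deviations describes follow-up for exploratory outcomes as optional and its deviations as not reportable to the IRB.

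**The concern.** Death is the most serious outcome of the disease and part of the trial's rationale. The records that would show it are already due for review at days 60, 90 and 120. Even so, no analysis compares deaths between arms.

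Two outcomes that are compared, length of stay and duration of ventilation, are cut short by death. Without a rule, an early death in hospital is recorded as a short value, which normally reads as favourable. A difference between arms in either outcome then has no clear meaning: it may reflect faster recovery, or more or earlier deaths. Analysing these durations in all randomized participants would not cure this, because an early death would still be scored as a short stay.

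**Working it through.** **1. The plan's own figure (background only).** The plan gives no mortality figure. Its sample size reproduces. With 14% v 9%, two-sided alpha 0.04, 80% power and 1:1 allocation (assumed), n per arm = [z₀.₉₈·√(2·p̄·(1−p̄)) + z₀.₈₀·√(p₁(1−p₁)+p₂(1−p₂))]² / 0.05², with p̄ = 0.115. That is [2.054·√0.2036 + 0.842·√0.2023]² / 0.0025, which rounds up to 682 per arm or 1364 in total, against the stated 1362. Nothing below changes it. Enrolment of 1500 gives 750 per arm and 750 × 0.14 = 105 expected placebo admissions.

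**2. Where each kind of death goes.**

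| Death | Primary outcome | Safety system | Stated by-arm comparison of deaths |
|---|---|---|---|
| COVID-19 death before hospitalization, first month | Event | SAE | Only inside the primary outcome |
| After a first-month COVID-19 admission | Already an event through the admission; death adds nothing | Admission of at least 24 hours is an SAE, followed under the Section 11 rule | None; lowers the discharge rate if it occurs in hospital and all admitted are the denominator |
| Fatal event with onset more than 30 days after last dose, not judged related | Not counted unless already an event | Need not be reported | None |

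For someone who completes 14 days, the recording window closes on day 14 + 30 = 44 from the start of treatment. The stretch to day 120 is at most 120 − 44 = 76 days. It is shorter in practice, because the 4 months run from the positive test, and consent and home delivery come before the first dose. Where treatment stops at admission, the window for new events closes 30 days after that stop, but the admission SAE is still followed.

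**3. Direction of the effect on stay.** Mean stay = (1 − m)·S + m·D, where m is in-hospital mortality, S is survivors' mean stay and D is mean stay in those who die. All values are assumed; the documents give none. With S = 10, D = 5 and m = 20% on RPS v 10% on placebo:
- RPS: 0.8 × 10 + 0.2 × 5 = 9.0 days
- Placebo: 0.9 × 10 + 0.1 × 5 = 9.5 days

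RPS looks half a day better with twice the mortality among those admitted. Varying D, and m on placebo over 5%, 10% and 20% (doubled on RPS):

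| D (days) | RPS minus placebo, mean stay (days) |
|---|---|
| 3 | −0.35 to −1.4 |
| 5 | −0.25 to −1.0 |
| 8 | −0.1 to −0.4 |
| 12 | +0.1 to +0.4 |
| 15 | +0.25 to +1.0 |

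The sign turns on whether D is below or above S. The same reasoning applies to ventilation time.

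**4. The discharge rate in the same scenarios.** With all admitted as denominator, discharge alive (placebo v RPS) is 95% v 90%, 90% v 80% and 80% v 60%. It moves against RPS every time. The plan fixes neither its denominator nor its time point, and it cannot register a death after discharge.

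**5. Precision of an all-randomized mortality comparison.** Half-width = 1.96·√(2·r·(1−r)/750), at assumed mortality r in both arms:

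| r | Half-width (points) | Added by a doubling (points) |
|---|---|---|
| 0.5% | 0.71 | 0.5 |
| 1% | 1.01 | 1.0 |
| 3% | 1.73 | 3.0 |

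With an observed difference of zero, a doubling is not excluded at 0.5% or 1%, but is at 3%. If 10% are lost (675 per arm), multiply by √(750/675) = 1.054, giving 0.75, 1.06 and 1.82.

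**The case against.** The plan covers more than a quick reading suggests, and four stronger inferences do not stand.

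- **That death after admission enters no comparison at all.** The Section 14 sentence goes on to discharge rates by arm. With all admitted as denominator, the 20% v 10% illustration gives 80% v 90% discharged, ten points against RPS beside the half-day shorter stay. This stands as a partial offset, limited by the missing denominator and time point.
- **That excess deaths would go unrecorded.** SAEs with onset in the window are recorded regardless of relationship and followed, potentially to death. They reach the DSMC, which may recommend stopping for observed harm. So it is not generally true that a COVID-19 death between about day 45 and day 120 is lost. The gap is confined to fatal events with late onset not judged related, and cases where follow-up ended on another satisfactory explanation. The absence of a by-arm split is silence in the plan, not a statement that none will be made.
- **That death necessarily shortens stay.** It does so only if those who die leave hospital sooner than survivors.
- **That the primary test is biased towards RPS.** A participant who dies after a first-month COVID-19 admission is already an event.

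It is also fair to say that the affected outcomes are exploratory with no allotted alpha, and that a mortality comparison would be imprecise. Both points limit the weight of the concern. Neither supplies the missing comparison or the missing rule.

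**Conclusion.** The point holds in a limited form. No by-arm mortality comparison is specified, although the rationale names mortality and EHR follow-up runs to death or 4 months. Fatal events with onset more than 30 days after the last dose and not judged related need not be reported and enter no stated analysis. Stay and ventilation duration have no rule for death, so they cannot be interpreted if deaths differ between arms.

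Under the assumptions shown (survivors 10 days, mortality doubled), the artefact in mean stay runs from 1.4 days in favour of RPS to 1.0 day against it, depending on time to death. A false benefit is therefore possible, not certain. The primary outcome and sample size are unaffected. This should be fixed because it is cheap and widens what the trial can report. It is not a defect in the main test.

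**What to change.** These changes concern analysis and data capture only.

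1. In Exploratory Objectives and Section 14, add all-cause death to 4 months (day 120) by arm in all randomized participants. Make it a descriptive safety comparison with a 95% CI and no alpha, using the EHR reviews already in Table 4.
2. In Protocol Deviations, exempt vital status from the wording that makes exploratory follow-up optional.
3. Replace length of stay and duration of ventilation with days alive and out of hospital and days alive and ventilator-free to day 120, counted from one stated origin. Alternatively, keep the durations and assign deaths the worst value.
4. Define the discharge outcome as discharged alive over all admitted, with a stated time point.

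The cost is wording and one table, with no added visits or participants. The downsides are few deaths and so a wide interval (about 0.7, 1.0 or 1.7 points either side at assumed mortality of 0.5%, 1% or 3%). Deaths outside the sites' records may also be missed in both arms. Making vital status mandatory adds some effort at the later EHR reviews.

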### **Randomization**

We will use stratified (by site) permuted block randomization and will generate randomization lists to be sent to the investigational pharmacy for packaging of starch and delivery to the designated participants.

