For our secondary outcomes, assuming a TTCA of about 14 days in the placebo group with standard deviation of 5 days, we calculated that a sample size of 196 would be required to provide 80% power (with a two-sided alpha level of 0.05) to detect an absolute reduction in TTCA by 2 days or more in the RPS group. For the outcomes of symptom severity score, we assumed that the placebo group would have a peak score of 20 with a standard deviation of 5 points, and we calculated that a sample size of 32 patients would be required to provide 80% power (with a two-sided alpha level of 0.05) to detect an absolute reduction in symptom severity score of 5 points or more in the RPS group.

Total accrual between all sites is 1500 patients. Depending on accrual rates, some sites may accrue more than other sites with a total goal of 1500 patients.

**Data analysis plan:** The primary outcome of hospital admission rates will be compared with the use of Pearson's chi-square test. The secondary outcomes of TTCA and symptom severity score will be compared in the two groups by means of a two-sample t-test. Adjusted measures and subgroup effects for the primary and secondary outcomes will be analyzed with the use of logistic regression and linear regression, respectively. Generalized estimating equations and linear mixed models will be used to test for an interaction between treatment group and

site in primary and secondary outcomes, respectively. The alpha level will be set at 0.05 for all analyses, 95% confidence intervals will be calculated, and all comparisons will be two-tailed.

*Interim analysis plans:*

Once our enrollment target for the secondary outcomes is reached (n~200), we will perform an interim analysis to assess safety, feasibility and treatment effect.

*Interim analysis 1(safety):*

All adverse events will be summarized and the independent data safety monitoring committee (DSMC) will make recommendations regarding continuation of recruitment. None of the DSMC members will be on our IRB protocol or the study team.

*Interim analysis 2 (feasibility):*

Study enrollment, follow up and any withdrawals from the study will be summarized and discussed by IDSMC to see if the degree of missing data is acceptable and if any further efforts need to be taken to optimize enrollment and follow up. Successful feasibility will be defined as more than 60% of patients took at least 50% of their prescribed doses (as directed by study team).

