*Interim analysis 3 (treatment effect):*

We will analyze the efficacy of RPS in relation to the primary outcome of hospitalization. If there is a significant difference between the two arm with p-value of <0.01, we will not continue the study. For data quality and integrity, we will also analyze the efficacy of RPS in relation to the secondary outcomes of TTCA and symptom severity score to assess efficacy and ensure no increase in harm in the intervention arm.

**Yale will be the central data analysis site.** All data will be analyzed by a full time statistician at the Program of Applied Translational Research.

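### Randomization is stratified by site but the primary chi-square and the secondary t-tests ignore site: valid tests that forgo a small, free gain

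*Combined protocol and SAP*

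**What the plan says.** The Randomization section states: "We will use stratified (by site) permuted block randomization". The Blinding section and the packaging and delivery section describe the same scheme.

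The data analysis plan in Section 14 then sets the main tests. For the primary outcome: "The primary outcome of hospital admission rates will be compared with the use of Pearson's chi-square test". For the others: "The secondary outcomes of TTCA and symptom severity score will be compared in the two groups by means of a two-sample t-test". Neither has a site term.

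Section 14 adds supporting analyses: "Adjusted measures and subgroup effects for the primary and secondary outcomes will be analyzed with the use of logistic regression and linear regression, respectively". No covariates are listed. Site is named only in the interaction analysis: "Generalized estimating equations and linear mixed models will be used to test for an interaction between treatment group and" site. The cluster unit and the variance estimator for the estimating equations are not given.

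The interim rule reads: "If there is a significant difference between the two arm with p-value of <0.01, we will not continue the study". It names no test, so the Pearson test presumably applies there too.

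**The concern.** Permuted blocks within site keep the arms balanced at each site. Differences between sites in baseline admission risk, or in mean recovery time, then cannot contribute to the treatment difference. An unstratified test still counts that variation in its standard error, which is therefore somewhat too large.

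There is some reason to expect such differences. The sites are meant to represent different regions, and each site's own principal investigator decides which admissions count as COVID-19 related.

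What is at stake is modest. Type I error does not rise above nominal and the planned power is not reduced. The loss is a little power and interval width that the design has already provided. In addition, with the adjusted covariates unnamed, whether site enters those models could be decided after the data are seen.

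**Working it through.** **Inputs from the documents.** Placebo admission rate 14%, reduction 5 points (so 9% on resistant starch), two-sided alpha 0.04, power 80%, 1362 evaluable, 1500 enrolled (Section 14, sample size). Alpha 0.05 in the data analysis plan. Time to recovery: SD 5 days, difference 2 days, n = 196. Symptom score: SD 5, difference 5, n = 32. Yale target 500 of 1500 (Section III); the Drug Information section and the Multicenter Coordinating Plan point to two sites.

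**Assumptions.** 1:1 allocation; a 1/3 : 2/3 split; site-specific rates and means, for which the documents give no figure; a common odds ratio across sites (0.58 to 0.61), solved to give 14% vs 9% overall.

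**Step 1: the plan's own figure.** Per arm, n = [z₀.₉₈√(2p̄(1−p̄)) + z₀.₈₀√(p₁(1−p₁)+p₂(1−p₂))]² / (p₁−p₂)², with p̄ = 0.115:

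[2.054 × √0.20355 + 0.842 × √0.2023]² / 0.05² ≈ 681.3, so 682 per arm and 1364 in total, against the stated 1362. It reproduces without any site term. At 681 per arm the power is 80.0%.

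**Step 2: what differs between the two tests.** Let X and Y be admissions by arm, and let site s have n_s patients and m_s admissions.

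- Pearson: (X−Y)² / [N p̄(1−p̄)]
- CMH, no continuity correction, 1:1 within site: (X−Y)² / Σ[m_s(n_s−m_s)/(n_s−1)]

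The numerators are identical. The Pearson denominator uses total variance; the CMH denominator uses within-site variance. If ρ is the between-site share of variance, Pearson type I error is approximately 2[1−Φ(2.054/√(1−ρ))] at alpha 0.04. With two sites, ρ = (1/3)(2/3)(gap)² / (0.14 × 0.86).

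- 8% vs 17%: ρ = 0.2222 × 0.09² / 0.1204 = 0.015, type I error 3.9%
- 5% vs 18.5%: ρ = 0.2222 × 0.135² / 0.1204 = 0.034, type I error 3.7%
- 24% vs 9%: ρ = 0.2222 × 0.15² / 0.1204 = 0.042, type I error 3.6%
- 30% vs 6%: ρ = 0.2222 × 0.24² / 0.1204 = 0.106, type I error 3.0%

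**Step 3: primary outcome by simulation** (400,000 trials per scenario; 454/908 patients at alpha 0.04, 500/1000 at alpha 0.05).

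| Placebo rates, site 1/site 2 | Pearson type I, 1362 | Pearson power, 1362 | CMH power, 1362 | Pearson power, 1500 | CMH power, 1500 |
|---|---|---|---|---|---|
| 14/14% | 4.0% | 80.2% | 80.1% | 86.2% | 86.2% |
| 8/17% | 3.9% | 80.3% | 80.7% | 86.5% | 86.7% |
| 5/18.5% | 3.7% | 80.7% | 81.5% | 86.6% | 87.2% |
| 24/9% | 3.6% | 80.6% | 81.7% | 86.7% | 87.4% |
| 30/6% (extreme) | 3.0% | 81.3% | 83.9% | 87.4% | 89.2% |

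CMH type I error was 4.0% throughout at 1362. Before rounding, the gain is 0 to 1.0 point outside the extreme case at 1362 and 0 to 0.7 point at 1500; in the extreme case it is 2.6 and 1.8 points.

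**Step 4: interval width at 1362.** Unstratified half-width: 1.96 × √[(0.1204 + 0.0819)/681] = 3.38 points. At 24/9% the odds ratio is about 0.60, which gives about 15.9% and 5.6% on active treatment. The mean within-site variances are then about 0.1154 and 0.0796, and the half-width is 1.96 × √[(0.1154 + 0.0796)/681] = 3.32 points.

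**Step 5: interim look** (66/134 patients, p < 0.01). Type I error is 0.92 to 0.96% for CMH and 0.63 to 0.98% for Pearson.

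**Step 6: secondary outcomes.** Total SD is held at 5. With site means 2.5 days apart and 66/130 patients, the within-site SD is √[25 − (66/196)(130/196)(2.5²)] = 4.86.

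| Gap between site means | t-test type I, n = 196 | t-test power, n = 196 | Power with site, n = 196 | t-test power, n = 32 | Power with site, n = 32 |
|---|---|---|---|---|---|
| 0 | 4.9% | 79.6% | 79.6% | 78.2% | 78.1% |
| 1 | 4.8% | 79.8% | 80.0% | 78.3% | 78.4% |
| 2.5 | 4.3% | 80.3% | 81.8% | 78.7% | 80.4% |

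Gaps are in days at n = 196 and score points at n = 32. If all 1500 are analysed, power for 2 days exceeds 99.99% either way. The half-width is 1.96 × 5 × √(2/750) = 0.51 day, or 0.49 day with site in the model at a 2.5-day gap.

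**The case against.** The case for leaving the plan alone is reasonable. The tests are valid, the stated 1362 already delivers 80% power with the unstratified test, and no stopping rule or conclusion changes. The gain rests on assumed site differences: a twofold gap (8% vs 17%) yields only 0.4 point, and the 2.6-point figure needs a gap that nothing in the documents supports. For the secondary outcomes, the gains at 196 and 32 patients matter little in a trial of 1500. The adjusted regressions may also be meant to include site.

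All of this bears on size and stands as a limit on it. It gives no reason to prefer the unstratified test: with equal site rates the two tests agree within 0.03 point of power, and with unequal rates CMH was better in every scenario. Leaving covariates unnamed does not place site in the adjusted models.

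A side issue is the interaction test. If the estimating equations took site as the cluster, with a fixed interaction term and a robust Wald test, each site's score contribution would be zero at the fit. The robust variance then vanishes: in 400 simulated trials with no interaction it rejected 99.5% of the time. The plan does not state that combination. Model-based variance rejected 3.5% and a logistic likelihood-ratio test 4.3%. No fault is shown in the mixed model. This is a request for clarity and does not carry the main point.

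**Conclusion.** The concern holds, as a small efficiency point. The main tests ignore the factor on which allocation is stratified. They remain valid as far as stratification goes, with type I error at or below nominal. The gain forgone on the primary outcome is 0 to about 1 point of power under moderate to large assumed site differences, and 2.6 points in the extreme case. For the secondary outcomes at full enrolment it is interval width only.

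The size depends on the assumed site rates, 1:1 allocation and the 1/3 : 2/3 split; the direction does not. Two other matters are not settled here: whether a t-test suits time to recovery, and the mismatch between alpha 0.04 in the sample size and 0.05 in the analysis plan.

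**What to change.** In the data analysis plan of Section 14:

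1. Make the Cochran-Mantel-Haenszel test stratified by site the primary test, with a site-stratified risk difference and 95% interval. Keep the Pearson chi-square as a sensitivity analysis.
2. Name the same CMH test for the interim efficacy look in Sections 13 and 14 and under Stopping Rules, so that both looks use one statistic.
3. Analyse time to recovery and symptom severity score with linear models that include site as a fixed factor, in place of the t-tests.
4. List site among the covariates of the adjusted logistic and linear regressions.
5. Optionally, label the treatment-by-site interaction test supportive and either state its cluster unit and variance estimator or use a likelihood-ratio test in ordinary logistic regression.

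The cost is wording. Site is already recorded for randomization; no patients, visits or data are added, the sample size stands, and type I error at the interim look stays below 1%.
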